6.1.3 Exploratory Efficacy Endpoints

CCI

CCI

6.1.4 Other Efficacy Variables: Non-Vaccine-Type (NVT) Pneumococcal Immunogenicity

In both Stage 1 Group 1 and Stage 2 Group 2, blood draws to determine SP1500+0785 levels (ng/mL) will be collected for subjects given either ASP3772 or PCV13. Levels of TH17 will be determined using an ELISpot assay and IL17 will be measured using a standard MSD ELISA. Levels of the following cytokines will also be assayed: IL-17, IL-22, CCI

6.2 Safety Endpoints

6.2.1 Adverse Events, Laboratory Values, Vital Signs, ECGs and Reactogenicity

For this study the primary endpoints address safety and tolerability of ASP3772. Safety and tolerability of ASP3772 will be assessed by:

- Treatment-emergent adverse events (TEAEs) including MAAEs, PIMMCs and NOCDs
- Laboratory assessments

- Vital signs (body temperature, blood pressure and pulse rate)
- Physical examination
- ECG
- Reactogenicity

6.2.1.1 Adverse Events

AE collection begins after the ICF has been signed and continues until screen failure, or for those enrolled, 30 days after study vaccine administration. A TEAE is defined as an AE observed after study immunization and up to 30 days post immunization. Medically attended adverse events (MAAEs) are AEs for which the subject has received medical attention by medical personnel, or in an emergency room, or which led to hospitalization. A new-onset chronic disease (NOCD), is defined as a MAAE which a) was absent at baseline; b) has not resolved at the follow-up telephone call; c) requires continuous medical care or attention.

PIMMCs are defined as any AEs of autoimmune or auto inflammatory nature. SAEs, MAAEs, which include PIMMCs and NOCDs, will be collected throughout the study, from vaccine administration on Day 1 up to the last follow-up visit (day 30 for Group 3; day 180 for Groups 1 and 2).

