7.5.1 Adverse Events

A TEAE is defined as an AE observed after study immunization and up to 30 days postimmunization. SAEs will be monitored for up to 180 days postimmunization (Group 1 and Group 2).

For each immunization arm, the frequencies and percentages will be displayed for the following TEAEs (coded using the Medical Dictionary for Regulatory Activities [MedDRA]) by system organ class and preferred term:

- Overall
- Serious
- Related (yes or no) to study vaccine

The number and percentage of subjects with TEAEs, SAEs, AEs and AEs related to study vaccine will be summarized by system organ class, preferred term and immunization group. The number and percentage of AEs by severity will also be summarized. MAAEs including PIMMCs and NOCDs, if any, will be summarized. All AEs will be listed.

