7.5.1 Adverse Events

AEs will be coded using the Medical Dictionary for Regulatory Activities (MedDRA). An overview table will include the following:

- Number and percentage of subjects with TEAEs
- Number and percentage of subjects with drug related TEAEs
- Number and percentage of subjects with serious TEAEs
- Number and percentage of subjects with serious drug related TEAEs
- Number of subjects with medically attended TEAEs (MAAEs)
- Number of subjects with potential immune mediated TEAEs (PIMMCs)
- Number of subjects with new onset chronic disease TEAEs (NOCDs)
- Number of deaths.

The number and percentage of subjects with TEAEs, classified by SOC, and PT will be summarized. Summaries (number and percentage of subjects) with each specific type of TEAE classified by SOC and preferred term will be provided for the following:

- TEAEs
- Drug-Related TEAEs,
- Serious TEAEs,
- Drug-Related serious TEAEs,
- TEAEs by Severity
- TEAEs leading to permanent discontinuation of study drug,
- Medically attended TEAEs (MAAEs)
- Potential immune mediated TEAEs (PIMMCs)
- New onset chronic disease TEAEs (NOCDs)
- Deaths

- Common (>=5% in any treatment group) Treatment-Emergent Adverse Events excluding Serious Adverse Events
- If a subject has multiple TEAEs with the same SOC or PT, the subject will be counted only once for the SOC and for an individual preferred term. For summaries by relationship, but with differing relationship (Yes, No), the subject will be counted only once for events with relationship equal to 'Yes'. If any of the relationship values are missing then the subject will be counted as having a related AE. A subject will be counted once under maximum severity. If severity is missing for all episodes of the event, the subject will be counted under the Missing category. Serious Adverse Events should not only include SAEs identified by the investigator on the eCRF, but also AEs upgraded by the Sponsor based on the Always Serious List (SAE flag on eCRF may not always be updated, but there will always be an SAE number in the eCRF database).

The following adverse events of special interest are defined:

- Reactogenicity

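### The SAP's summaries of serious, medically attended, immune-mediated and new chronic events are labelled as TEAEs, so as written they stop at Day 30 although these events are collected to Day 180

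*SAP*

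**What the plan says.** **Window.** SAP 6.2.1.1 states: "A TEAE is defined as an AE observed after study immunization and up to 30 days post immunization". Protocol 7.5.1 gives the same 30 days.

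**Collection.** SAP 6.2.1.1 also says that "SAEs, MAAEs, which include PIMMCs and NOCDs, will be collected throughout the study", ending at Day 180 for Groups 1 and 2 and at Day 30 for Group 3. Protocol 7.5.1 has SAEs monitored to 180 days in Groups 1 and 2.

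**SAP summaries.** In SAP 7.5.1 the overview table includes "Number and percentage of subjects with serious TEAEs". The rows for drug-related serious events, MAAEs, PIMMCs and NOCDs carry the TEAE label in the same way. The tables by system organ class and preferred term are introduced as summaries "with each specific type of TEAE classified by SOC and preferred term will be provided for the following", and the entries for these five items again say TEAE.

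**Protocol summaries.** Protocol 7.5.1 has a display of TEAEs that includes a serious category. It then adds: "The number and percentage of subjects with TEAEs, SAEs, AEs and AEs related to study vaccine will be summarized". It also says: "MAAEs including PIMMCs and NOCDs, if any, will be summarized". Neither of these two sentences limits SAEs or MAAEs to TEAEs.

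**A conflicting statement.** Protocol 5.4.1 has TEAEs, as well as MAAEs, assessed from dosing to the last follow-up visit, which is Day 180 for Groups 1 and 2.

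**The concern.** The 30-day definition is not itself the problem, since both documents use it. The problem is that SAP 7.5.1 applies it to the event classes for which follow-up was extended to Day 180. A programmer who derives the TEAE flag as defined and builds the tables as labelled will drop every non-fatal SAE, MAAE, PIMMC and NOCD that starts after Day 30.

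Safety and tolerability against PCV13 is the primary objective in both stages. SAP 6.2.1 names TEAEs including MAAEs, PIMMCs and NOCDs as a primary safety measure, and Protocol 7.5 adds SAEs. For a first-in-human vaccine, the long follow-up exists to detect late serious, immune-mediated and chronic events. Without an arm-level summary, those events could be compared by dose with PCV13 only by reading listings.

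Timing adds to the concern. Under SAP 7.6 the sponsor is unblinded at each stage's Day 30 cut-off, while follow-up to Day 180 continues. If the window is left open, the sponsor would decide how to tabulate Day 31 to 180 events after seeing treatment assignments.

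**Working it through.** The plan states no figure on this point to reproduce. The check is a comparison of text, followed by simple arithmetic on follow-up time.

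**Step 1. Windows**

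| Item | Groups 1 and 2 | Group 3 | Source |
|---|---|---|---|
| TEAE definition | to Day 30 | to Day 30 | SAP 6.2.1.1; Protocol 7.5.1 |
| SAE and MAAE (with PIMMC, NOCD) collection | to Day 180 | to Day 30 | SAP 6.2.1.1 |
| TEAE assessment period | to Day 180 | to Day 30 | Protocol 5.4.1 |

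**Step 2. Count of affected summaries in SAP 7.5.1**

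| Display | Items | Day 180 categories labelled TEAE |
|---|---|---|
| Overview table | 8 | 5: serious, serious drug-related, MAAE, PIMMC, NOCD |
| Tables by system organ class and preferred term | 11 | the same 5 |

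Total affected: 5 + 5 = 10.

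**Step 3. Search for another summary that would catch late events**

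- The overview row for deaths has no TEAE label, so a late death can appear there.
- SAP 7.2.1 tabulates discontinuations between Day 30 and Day 180, including those for an adverse event or death. This is a disposition table.
- Protocol 7.5.1 lists all AEs. This is a listing.
- The SAP 7.5.1 sentence on sponsor-upgraded SAEs settles which events count as serious, not the period.
- SAP 3.3 says more safety information is gathered at Day 180 but attaches no summary to it.

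None of these is an arm-level summary of non-fatal late SAEs, MAAEs, PIMMCs or NOCDs.

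**Step 4. Consistency with the NOCD definition.** Both documents require an NOCD to be unresolved at the follow-up telephone call. In Groups 1 and 2 the scheduled telephone contact is the Day 180 visit. The SAP therefore uses Day 180 information to classify an NOCD but, by its label, counts only those that began by Day 30.

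**Step 5. Follow-up time outside the window**

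Inputs: 120 subjects planned in Group 1, 396 in Group 2, 99 per ASP3772 dose arm in Stage 2. Dropout is ignored.

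- Share of follow-up: (180 − 30) / 180 = 150 / 180 = 83.3%.
- Groups 1 and 2: 120 + 396 = 516 subjects. Outside the window: 516 × 150 = 77,400 subject-days. Total: 516 × 180 = 92,880 subject-days.
- In years: 77,400 / 365.25 = 211.9 and 92,880 / 365.25 = 254.3.
- One Stage 2 dose arm: 99 × 150 = 14,850 subject-days, and 14,850 / 365.25 = 40.7 subject-years.
- Group 3: none, because its follow-up ends at Day 30.

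**Step 6. Illustration in events (assumed rates).** The documents give no rates. Assume a Day 180 cumulative risk p180 of 2%, 5% or 10% and a constant hazard, so that p30 = 1 − (1 − p180)^(30/180). The chance of at least one event in a 99-subject arm is 1 − (1 − p)^99.

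| p180 | p30 | Group 2 subjects with an event by Day 180 (396 × p180) | By Day 30 (396 × p30) | At least one in 99 by Day 180 | By Day 30 |
|---|---|---|---|---|---|
| 2% | 0.34% | 7.9 | 1.3 | 86% | 28% |
| 5% | 0.85% | 19.8 | 3.4 | 99% | 57% |
| 10% | 1.74% | 39.6 | 6.9 | >99.9% | 82% |

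If events cluster soon after vaccination the loss is smaller. If they arise late it is larger.

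**The case against.** **The protocol is not uniformly wider.** Protocol 7.5.1 itself has a TEAE display with a serious category, and Protocol 7.5 places SAEs, MAAEs, PIMMCs and NOCDs inside TEAEs. This is true, and it shows the conflict also runs through the protocol. But the same protocol section goes on to plan summaries of SAEs and of MAAEs with no TEAE limit, and the SAP has no counterpart to these. The SAP remains the narrower document.

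**The intent may have been to include late events.** Protocol 5.4.1 carries TEAEs to Day 180, and the NOCD definition needs the telephone call. Both suggest that late data were meant to reach these rows. That may be so, but the explicit definition says 30 days in both documents. The argument is weakest for the serious-event rows, which have no separately defined category name beside the TEAE label. The table specifications named in SAP 7.1 are not among the documents, so what will actually be programmed is unknown. The SAP text should decide it.

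**No data are lost and no test is affected.** Collection and expedited SAE reporting run to Day 180, all AEs are listed, deaths are counted, and these AE summaries are descriptive. All of this stands, and it is why the correction is cheap. It does not supply the by-dose comparison with PCV13 that the primary objective calls for.

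**The size is in time, not events.** This also stands. The 83% measures follow-up days, and the event illustration depends wholly on assumed risks and a constant hazard.

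**Conclusion.** The concern holds. Read as written, 10 summaries in SAP 7.5.1 exclude SAEs, MAAEs, PIMMCs and NOCDs that start on Days 31 to 180 in Groups 1 and 2. Only the deaths row offers an arm-level event count beyond Day 30. The excluded period is 83% of scheduled follow-up, about 212 of 254 subject-years at the planned 516 subjects with no dropout. How many events this represents cannot be said from the documents. The conclusion rests on applying the stated TEAE definition to rows that carry the TEAE label. Protocol 5.4.1 does not remove the problem: it gives a second, incompatible window for a primary safety measure. This is an error in the stated rule rather than missing detail, and it should be corrected before the tables are programmed and before any further unblinding.

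**What to change.** 1. Keep the 30-day TEAE window for other unsolicited AEs.
2. In SAP 6.2.1.1 and 7.5.1, define the summaries of SAEs, drug-related SAEs, MAAEs, PIMMCs, NOCDs and deaths over immunization to the last follow-up visit: Day 180 for Groups 1 and 2, Day 30 for Group 3. Remove the TEAE label from those rows and tables. A split at Day 30 within each is optional.
3. Reconcile Protocol 5.4.1 with Protocol 7.5.1 and SAP 6.2.1.1 so that one TEAE window is stated.

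This delivers the summaries that Protocol 7.5.1 already plans. It costs SAP wording, revised table shells and a clarification in Protocol 5.4.1. No new data are needed.

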6.2.1.2 Laboratory Values

Laboratory safety assessments will be collected at the screening visit and at study immunization if screening was performed > 7 days from study immunization [day 1]. Assessments will be repeated at follow-up visits on day 7 and day 30. These include the following:

- Hematology (hemoglobin, hematocrit, erythrocytes, leukocytes, differential WBC, platelets),
- Biochemistry (sodium, potassium, calcium, chloride, glucose, total cholesterol, triglycerides, blood urea nitrogen, creatinine, creatine kinase, uric acid, total protein, albumin, c-reactive protein),
- Coagulation profile (prothrombin time, activated partial thromboplastin time, fibrinogen)
- Hepatic profile (alkaline phosphatase, aspartate transaminase, alanine transaminase, γ -glutamyltransferase, total bilirubin, lactate dehydrogenase),
- Urinalysis (using dipstick - protein, glucose, pH, blood, leukocytes, urobilinogen, bilirubin, ketones, nitrite)
- Urine microscopy [optional] (casts, crystals, epithelial cells, leucocytes, erythrocytes, bacteria).
- Pregnancy Testing (Human Chorionic Gonadotropin (hCG))

Laboratory assessments assayed at baseline to determine eligibility are:

- Drug screening (amphetamines, barbiturates, benzodiazepines, cannabinoids and cocaine)
- Virology (Anti-HAV (IgM), HBsAG, Anti-HBc, Anti-HCV, Anti-HIV-1 and 2

Laboratory values collected on Days 7 and 30 will be categorized programmatically using the definitions in Appendix D: Grading Laboratory Abnormalities for Healthy Adult Subjects.

These post vaccination laboratory values are categorized into 4 grads of reactogenicity.

6.2.1.3 Vital Signs

Vital sign measurements will be taken for one hour post immunization to assess systemic reactions to the immunization. Each of these will be graded and reported according to the definitions contained in the table below.

Vital Signs	Mild (Grade 1)	Moderate (Grade 2)	Severe (Grade 3)	Potentially Life-threatening (Grade 4)
Fever (°C)‡ (°F)‡	38.0-38.4 100.4-101.1	38.5-38.9 101.2-102.0	39.0-40 102.1-104	>40 >104
Tachycardia (bpm)	101-115	116-130	>130	ER Visit or hospitalization for arrhythmia
Bradycardia (bpm)	50-54	45-49	<45	ER Visit or hospitalization for arrhythmia
Hypertension (systolic) (mm Hg)	141-150	151-155	>155	ER visit or hospitalization for malignant hypertension
Hypertension (diastolic) (mm Hg)	91-95	96-100	>100	ER visit or hospitalization for malignant hypertension
Hypotension (systolic) (mm Hg)	85-89	80-84	<10	ER visit or hospitalization for hypotensive shock
Respiratory Rate (breaths per min)	17-20	21-25	>25	Intubation

bpm: beats per minute; ER: emergency room

† Subject should be at rest for all vital sign measurements.

‡ Oral temperature; no recent hot or cold beverages or smoking.

§ When resting heart rate is between 60 and 100 bpm. Use clinical judgment when characterizing bradycardia among some healthy subject populations, e.g., conditioned athletes.

6.2.1.4 Physical Examinations

Physical examinations will be performed prior to dosing and at Day 30 post immunization.

6.2.1.5 ECGs

ECGs will be collected at screening for all groups at Screening for all groups and at Day 7 for Groups 1 and 2, those randomized to PCV13 or ASP3772. ECGs will be graded as ‘normal’, ‘abnormal-not clinically significant’, and ‘abnormal-clinically significant’. Any abnormal ECGs that have worsened since screening/baseline will be recorded as an adverse event.

6.2.1.6 Reactogenicity

Reactogenicity will be assessed using daily solicited adverse reactions and the daily maximum value will be recorded in an electronic diary for up to 7 days post immunization. These include local and systemic reactions with a predefined grading scale (see Section 10.2,

Appendix B: **Local Reactogenicity Grading** and Section 10.3, Appendix C: **Grading Signs of Systemic Reactogenicity**; and Section 10.4, Appendix D: **Grading of Laboratory Abnormalities**). Local reactions are pain, tenderness, redness/erythema, swelling and induration. Systemic reactions are nausea/vomiting, diarrhea, headache, fever, fatigue and muscle discomfort or pain/myalgia. Subjects in stage 1 will be asked to report joint pain/arthritis through day 7 postimmunization during the day 7 visit. This addition was requested by the FDA after the electronic diary was being used at the sites. The ePRO device will be revised for Stage 2 so that subjects will be asked to report symptoms of arthritis daily for 7 days post immunization.

Reactogenicity reactions will be reported as Clinical Events. If the reactogenicity reaction extends beyond 7 days or if serious, it will also be recorded as an AE.

6.3 Pharmacokinetic Variables

Not applicable.

6.4 Pharmacodynamic Variables

Not applicable.

6.5 Other Variables

Samples for anti-biotin antibodies will be collected before immunization, at Day 30 and if positive at Day 30, at Day 180 for subjects in Stage 1, Group 1 and Stage 2, Group 2. Biotin levels will be measured in the same sample if the sample is positive for anti-biotin.

7 STATISTICAL METHODOLOGY

7.1 General Considerations

For continuous variables, descriptive statistics will include the number of subjects (n), mean, standard deviation, median, minimum, maximum, when applicable, or the geometric mean (GM) and geometric standard deviation (GSD). The geometric mean ratio (GMR) and 95% confidence interval (CI) will be used to compare the response following each dose of ASP3772 (1, 2, or 5 µg) to PCV13 within each stage. Calculations for the GM, the GMR and the geometric mean fold rise (GMFR) with the associated GSD and 95% CI can be found in Section 10.1, Appendix A: **Instructions to calculate the Summary statistics for the secondary endpoints**. Frequencies and percentages will be displayed for categorical data by treatment group (ASP3772 (1 µg, 2 µg, 5 µg) or PCV13) and stage. Percentages by category will be based on the number of subjects without missing data. Subjects with missing data will be treated as a separate category and not included in the denominator, unless specific methods for imputation are stated.

Summaries based on FAS and PPS (if needed) (e.g. disposition, baseline and efficacy data) will be presented by treatment group (ASP3772 (1 µg, 2 µg, 5 µg) or PCV13) and stage. All subjects treated with PCV13 will be combined according to their age group (Stage 1: Adults,

Stage 2: Elderly 65-85, 65-74 and 75-85). Data for all PPSV23 enrolled subjects will be summarized separately.

For serotypes common to PCV13 and ASP3772, the following treatment group comparisons for immunogenicity are of interest to determine the magnitude of the response following ASP3772 relative to PCV13 for each serotype within adults 18-64, within elderly 65-85 and within elderly subgroups 65-74 and 75-85.

- ASP3772 1 μ g vs PCV13
- ASP3772 2 μ g vs PCV13
- ASP3772 5 μ g vs PCV13

For all serotypes unique to ASP3772, the comparison will be post-dose relative to pre-dose.

Safety analyses and other summaries based on the SAF will be presented by treatment group (ASP3772 (1 μ g, 2 μ g, 5 μ g) or PCV13) and stage (adults 18-64 years, elderly 65-85 years). Within the elderly cohort summaries will also be provided where indicated for those 65-74 and those 75-85. All adult PCV13 subjects will be combined into a single group and all elderly PCV13 subjects will be combined into a single group consistent with the age group being analyzed. Summaries for all PPSV23 enrolled subjects will be provided separately.

All statistical comparisons will be made using two sided tests at the $\alpha=0.05$ significance level unless specifically stated otherwise and 95% confidence intervals will be provided. All null hypotheses will be of no treatment difference; all alternative hypotheses will be two-sided, unless specifically stated otherwise.

All data processing, summarization, and analyses will be performed using SAS®Version 9.1.3 or higher on Unix. Specifications for table, figures, and data listing formats can be found in the TLF specifications for this study.

7.2 Study Population

7.2.1 Disposition of Subjects

The following subject data will be presented:

- Disposition: number of subjects with informed consent, discontinued before randomization, randomized and immunized;
- Analysis sets: number and percentage of subjects in the safety analysis set (randomized and received an immunization, full analysis set (randomized, immunized, and at least 1 post baseline endpoint evaluation) and per protocol analysis set (if needed) (subjects who did not receive antibiotics within 7 days of their Day 30 blood draw; subjects who have their Day 30 blood draw between Day 30 and Day 44; subjects who have not received immunosuppressants; subjects who do not have newly diagnosed immunologic abnormalities within the first 2 weeks after receiving the immunization);
- Treatment discontinuation: number and percentage of randomized subjects who completed and who discontinued treatment, by primary reason for treatment discontinuation (adverse event, death, lost to follow-up, protocol deviation, withdrawal by subject, other);

- Discontinuation up to 30 days: number and percentage of randomized subjects who completed and who discontinued the 30-day investigational period, by primary reason for discontinuation (adverse event, death, lost to follow-up, protocol deviation, withdrawal by subject, other);
- Discontinuation after Day 30 up to Day 180: Number and percentage of randomized subjects who completed and who discontinued during the follow-up period (post Day 30 through Day 180), by primary reason for discontinuing during the follow-up period (adverse event, death, lost to follow-up, protocol deviation, withdrawal by subject, other); subjects in Group 3 will not be followed beyond Day 30.
- Per protocol exclusions: Number and percentage of subjects excluded from PPS by reason for exclusion defined in Section 5.2, by treatment group.

7.2.2 Protocol Deviations

The number and percentage of subjects who met the following protocol deviation criteria will be summarized for each criterion and by study site. Subjects deviating from a criterion more than once will be counted once for the corresponding criterion. Any subjects who have more than one protocol deviation will be counted once in the overall summary. A data listing will be provided by site and subject.

The protocol deviation criteria will be uniquely identified in the summary table and listing. The unique identifiers will be as follows:

- PD1 - Entered into the study even though they did not satisfy entry criteria,
- PD2 - Developed withdrawal criteria during the study and was not withdrawn,
- PD3 - Received wrong treatment or incorrect dose,
- PD4 - Received excluded concomitant treatment.

